5.0 Number of Subjects

Twenty adults (≥ 18 years old) with spastic hyperreflexia due to stroke are recruited from the community around the MUSC and a greater Charleston area.

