7.0 Recruitment Methods

Adults (≥ 18 years old) with spasticity due to stroke are recruited from the community around the MUSC and greater Charleston area. Individuals with stroke will be recruited through word of mouth (i.e. support group meetings, through clinicians, health care providers, and participants). Subjects recruited in this manner will be directed to contact the research team directly. This study will also recruit from the Registry for Stroke Recovery (RESTORE-Pro#00037803, IRB approved 9/6/14) which is a research tool sponsored by the National Institutes of Health (NIH) Center of Biomedical Research Excellence (COBRE) in Stroke Recovery with subjects consented for future contact to support stroke recovery research conducted at MUSC. RESTORE staff will query the registry for potential subjects and provide the Principal Investigator (PI) with the contact information of subjects who meet their criteria. The PI or research staff will contact subjects via phone or email to further screen for potential enrollment.

The research coordinator will be the first study staff to make the contact with a potential participant, obtain the medical records, and pre-screen him/her for eligibility. During this process, the coordinator will mail or email the study consent form to the potential participant. For medical/neurological screening of participants, the pre-screened potential participant will be brought to MUSC for an appointment with the study therapist and investigators, if agreed. The coordinator will obtain the signed consent from the potential participant in person, prior to the in-person medical or EMG screening (i.e., first preliminary session).

The participant will be paid \$45 for the second and fifth sessions, and \$15 for the remaining 5 sessions. S/he will also be provided with transportation reimbursement if needed. The participant will be reimbursed \$0.56 per mile for transportation costs for any distance greater than or equal to 1 mile; or if s/he is using a transportation service (CARTA, etc.), the fee may be reimbursed. The payment (including transportation expense) will be made with cash or ClinCard, even if the participant does not complete the sessions.

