9.0 Study Design / Methods

This study is a partial cross-over waitlist control design, in which each of the 20 participants post stroke will participate in 7 visits over a two-week period, during which measurements will be taken 10 times. Neurophysiological and functional measurements will be collected five times over 3 visits during the first week (treatment as usual control week), through which each participant will serve as their own "controls" for their second week of measurements. No sham or other treatment procedure will occur during this week. On the second week, all participants will transition to the DDN intervention week where five measurements will be collected over 3 visits (one pre-DDN baseline and four post-DDN measurements: immediately after, 90 minutes, 24 hours, and 72 hours).

Deep Dry Needling (DDN)

DDN procedures used in this project have been widely used in clinical practice to treat spasticity and pain in individuals with neurological and non-neurological (orthopedic) injuries [15,16,18,20,21,48,75].

Each participant receives a single session of DDN, targeting the medial gastrocnemius. In each DDN session, first, localized hypersensitive spots in palpable taut bands of the targeted skeletal muscles (i.e., MTrPs)(75, 76) are identified with pincer palpation. Then, after cleaning the skin area over a MTrPs with alcohol swabs, a disposable stainless steel acupuncture needle is inserted into the skin, penetrating approximately 15 to 20 mm to the depth of the trigger point, until the local twitch response (LTR) is elicited. Once the LTR is confirmed, the needle is moved up and down

(~4-5 mm vertically) with a small piston motions (approximately at 1 Hz for 25 to 30 seconds) with no rotation at the MTrPs (9,10, 38). The same procedure is repeated at other MTrPs in the same local skin region as needed until the LTR is eradicated. After removing the needle, the needled area is rubbed to prevent bleeding and bruising. Each participant will complete 5 repetitions of each of the following: ankle plantarflexion/dorsiflexion passive range of motion (PROM), sub-maximal concentric and eccentric contractions of the plantarflexors as would be typical in a clinical setting.

Electromyography (EMG) and nerve stimulation

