At the beginning of each session, surface self-adhesive Ag-AgCl electrodes are placed over the TA, medial and lateral gastrocnemius (MG and LG), and soleus muscles of the studied leg. Throughout the study, all EMG activity is amplified, band-pass filtered (10-1000 Hz), sampled at 3,200 Hz, and stored. Nerve stimulation protocol consists of 4 components: (1) single pulse posterior tibial nerve stimulation for the triceps surae H-reflex / M-wave (H/M) recruitment curve measurement, (2) single pulse common peroneal (CP) nerve stimulation for the TA H/M recruitment curve measurement, (3) multiple pulse (train) tibial nerve stimulation for cutaneous reflex measurement, and (4) multiple pulse (train) superficial peroneal (SP) nerve stimulation for cutaneous reflex measurement.

- (1) ***Single pulse posterior tibial nerve stimulation for triceps surae H/M recruitment curve:*** To elicit the triceps H-reflex, the tibial nerve is stimulated in the popliteal fossa, using surface Ag-AgCl electrodes and isolated constant current stimulation. The stimulating electrode pair is placed so as to minimize the H-reflex threshold and to avoid stimulation of other nerves. For eliciting the H-reflex and M-wave, a 1-ms square stimulus pulse is delivered when the participant has maintained his/her natural standing level (typically, 10-20% of maximum voluntary contraction (MVC) level of EMG activity) of soleus EMG activity for at least 2 s. The minimum interstimulus interval is 5 s. An H/M recruitment curve is obtained by gradually increasing the stimulus intensity in increments of 1.2-2.5 mA from the H-reflex threshold to the maximum H-reflex (H_{max}) to an intensity just above what is needed to elicit the maximum M-wave (M_{max}) [77-79], while the participant stands and maintains the above noted level of soleus EMG activity. About 10 different intensities are used to obtain a recruitment curve, and four EMG responses are averaged to measure the H-reflex and M-wave at each intensity. Then, about 100 responses are elicited at the H_{max} level of stimulus intensity (i.e., weak to mild intensity) while monitoring cortical electroencephalographic (EEG) activity.

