10.0 Data Management

Data analysis: Reflex sizes are calculated in reference to each participant's M_{max} measured during natural standing. For example, the peak-to-peak H-reflex amplitude is normalized to the peak-to-peak M_{max} amplitude, and the mean rectified H-reflex amplitude is normalized to the mean rectified M_{max} amplitude.

For comparing reflex sizes before and after dry needling, a two-way repeated measures ANOVA (studied side of the extremity \times time) will be used, together with Student t-test with Bonferroni correction as a post-hoc test. For simple comparison between participants without known neurological conditions and participants after stroke (e.g., age and M_{max}), and assessments of changes in sensory and motor function (i.e., only applicable to participants after stroke), a Student t-test will be used.

Data management: The data will be managed by the PIs and research coordinator at the College of Health Professions (CHP). All EMG and assessment data are electronically stored in the secure CHP server with password protection. Only the investigators directly involved in this project have access to these data.

Protection of participant confidentiality is essential in human clinical trials. The participants' confidential information will be securely stored in locked cabinets of a locked room and a password-protected computer, and only the principal and co-investigators and the research coordinator will have access to the participant's confidential information. For the length of the study, limited personal information (specifically, the participant's name, address, and social security number) will also be accessible to the program administrator for processing the participant reimbursement paperwork. Investigators and therapists, who run data collection sessions, will have access to the EMG and other collected data for the purpose of analysis, but will have no access to the participant's confidential information. Alphanumeric codes will be assigned to each participant's dataset to protect confidentiality.

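### The repeated-measures ANOVA has no sphericity correction and no rule for missed visits, although three of each week's five measurements share a visit and the other two do not

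*Combined protocol and SAP*

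**What the plan says.** The data analysis text in section 10.0 (Data Management) gives one model for the reflex outcomes: "For comparing reflex sizes before and after dry needling, a two-way repeated measures ANOVA", with studied side and time as factors and Bonferroni-corrected Student t-tests post hoc. It names no sphericity test or correction, covariance structure, analysis set or missing-data rule, and neither does any other section. It does not say whether time has five levels or ten, or whether the t-tests use the ANOVA's pooled error or each pair's own error.

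The design is in sections 5.0 and 9.0. The sample is "Twenty adults (≥ 18 years old) with spastic hyperreflexia due to stroke". Of the schedule, section 9.0 says "each of the 20 participants post stroke will participate in 7 visits over a two-week period", "during which measurements will be taken 10 times". The control week has five measurements in three visits, and in the DDN week "five measurements will be collected over 3 visits". The pre, immediate and 90-minute measurements fall on one day; 24 h and 72 h are separate visits. Section 1.0 matches the control-week intervals to these. On recording: "At the beginning of each session, surface self-adhesive Ag-AgCl electrodes are placed".

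On completion, section 7.0 pays participants "even if the participant does not complete the sessions". Sections 11.0 and 12.0 let them stop any part of the study, and section 12.0 notes that some may find DDN stressful or painful.

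**The concern.** A classical repeated-measures ANOVA depends on two conditions that the plan does not address.

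The first is sphericity: all pairwise differences between time points have the same variance. Measurements within one visit share electrodes and the participant's state that day, so their differences should vary less than differences between visits. If so, the uncorrected F test rejects too often. Any post-hoc contrast built on the pooled ANOVA error has the wrong standard error: too small across visits, too large within a visit. That matters for a study of whether an effect is immediate or lasts to 72 h.

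The second is complete data. Standard software drops a participant who lacks one time point. With 20 participants each loss costs precision, and people who stop after an unpleasant needling may differ from those who continue.

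**Working it through.** **The plan's own figure.** The sample size of 20 cannot be reproduced. No alpha, power, effect size, SD, correlation or dropout rate is stated. Everything below uses n = 20 and the visit schedule from the protocol. The correlations, missed-visit rates and two-sided alpha of 0.05 are assumptions.

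**1. Omnibus F test for time.** Time points sit on days 0, 0, 0, 1, 3 (five levels), or in that pattern in both weeks (ten levels), with equal variances. Departure from sphericity is measured by epsilon = [tr(PSP)]² / {(k − 1) tr[(PSP)²]}, where S is the covariance matrix, k the number of levels and P the centring matrix; epsilon = 1 means sphericity. A one-way repeated-measures ANOVA was simulated under the null, 20,000 runs per row.

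| Same-visit / cross-visit correlation | epsilon, 5 levels | Type I error, 5 levels | epsilon, 10 levels | Type I error, 10 levels |
|---|---|---|---|---|
| 0.70 / 0.70 | 1.00 | 5.1% | 1.00 | 5.0% |
| 0.80 / 0.70 | 0.93 | 5.5% | 0.90 | 6.2% |
| 0.90 / 0.70 | 0.72 | 6.8% | 0.67 | 8.1% |
| 0.90 / 0.50 | 0.61 | 8.3% | 0.57 | 9.4% |
| 0.95 / 0.50 | 0.54 | 8.8% | 0.50 | 10.1% |

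The simulation error is small: √(0.05 × 0.95 / 20,000) = 0.0015, or about 0.15 percentage points. Across these rows the Greenhouse-Geisser F stays at 3.9-4.7% for five levels and 2.4-4.0% for ten. Bonferroni paired t-tests against the pre value, each with its own error, have a familywise error of 3.8-4.7%.

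**2. Post-hoc contrasts on the pooled error.** With unit variances, the expected ANOVA error is 1 − r̄, where r̄ is the mean of the ten pairwise correlations: three same-visit and seven cross-visit. At 0.90 / 0.70:

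- r̄ = (3 × 0.90 + 7 × 0.70) / 10 = 0.76
- assumed variance of any difference: 2 × (1 − 0.76) = 0.48
- true cross-visit variance: 2 × (1 − 0.70) = 0.60, so the standard error is √(0.48 / 0.60) = 0.89 of the correct size
- true same-visit variance: 2 × (1 − 0.90) = 0.20, so the standard error is √(0.48 / 0.20) = 1.55 times the correct size

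In simulation (same-visit 0.90-0.95, cross-visit 0.5-0.7), pooled contrasts of pre against 24 h or 72 h at the Bonferroni level of 0.05 / 4 = 0.0125 reject 2.6-3.7% of the time. Same-visit contrasts reject less than 0.1% of the time.

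**3. Complete cases.** If each visit is missed independently with probability p, the expected number complete over v visits is 20 × (1 − p)^v.

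- Three DDN-week visits: 20 × 0.99³ = 19.4; 20 × 0.98³ = 18.8; 20 × 0.95³ = 17.1
- Six visits in both weeks: 20 × 0.99⁶ = 18.8; 20 × 0.98⁶ = 17.7; 20 × 0.95⁶ = 14.7

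**4. Precision.** From the noncentral t distribution (paired t-test, 80% power), the detectable effect is 0.66 SD of the paired difference at n = 20 and 0.72 SD at n = 17. An effect of 0.66 SD has 72.5% power at n = 17.

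**The case against.** A reader might infer three stronger statements that the documents do not support.

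- **That the plan drops everyone with a missed visit.** No section says so. It is the method's usual default, and the plan is silent.
- **That five or six of the 20 will be lost.** The text in section 7.0 is a payment clause, and the right to stop is standard; neither forecasts non-completion. A loss of five or six needs, for example, 5% missed over six visits (20 − 14.7 = 5.3) or 10% over three (20 − 20 × 0.90³ = 5.4). The analysis sentence most naturally refers to the three DDN-week visits. If misses cluster in the same people, fewer participants are affected: with an assumed intraclass correlation of 0.2, 16.3 rather than 14.7 of 20 are complete at 5% over six visits.
- **That the trial's false-positive rate is raised throughout.** Paired t-tests with their own error do not need sphericity, and they answer the pre/post question directly. Only the uncorrected omnibus F, and contrasts on its pooled error, are affected.

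The size of the violation is also open. Section 10.0 normalises reflexes to Mmax, which should remove part of the electrode-placement effect. With correlations as close as 0.8 and 0.7, the five-level error is 5.5%, near nominal. Normalisation cannot remove day-to-day change in reflex excitability, so some violation remains likely. The formal assumption is sphericity; equal correlations with equal variances are sufficient for it, not necessary. The simulation covers the time effect only, not side by time. This is also a pilot.

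These points limit the size of the problem. The plan still addresses neither condition that its model depends on.

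**Conclusion.** The point holds as a gap in the specification, with a modest and conditional effect. The visit schedule makes sphericity implausible, and no correction is named. If the F test is left uncorrected, its type I error is about 5.5-9% for five time levels and 6-10% for ten, given same-visit correlations of 0.8-0.95, cross-visit correlations of 0.5-0.7 and equal variances. Pooled-error contrasts would be too liberal across visits and too conservative within a visit. Paired post-hoc tests with their own error are sound.

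The cost of missed visits cannot be fixed from the documents. At 1-5% missed independently, the number complete falls to 19.4-17.1 over the DDN week, or 18.8-14.7 if both weeks must be complete. Over a two-week study it could stay at 20.

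**What to change.** In section 10.0, replace the ANOVA with a linear mixed model for reflex size, fitted by REML with Kenward-Roger or similar small-sample degrees of freedom. Use every available measurement, treat time as categorical, and include random effects for participant and for visit within participant. Estimate the four post-versus-pre contrasts from this model. State that it is valid under missing at random and does not cure dropout that depends on unobserved response. Report how many participants miss each visit, and why.

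If the ANOVA is kept, state the number of time levels, apply the Greenhouse-Geisser correction, run the post-hoc t-tests as paired tests with their own error term, and write down how missed visits are handled.

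Either change costs only a revision of the analysis text and uses standard software. No new data, visits or participants are needed.

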Available small studies, case reports (14-22), and our preliminary data (87) support that DDN likely produces neural plasticity at both spinal and supraspinal levels. Thus, our central hypothesis is that ***DDN at MTrP induces plasticity in the spinal and supraspinal pathways and produces therapeutic effects.*** While the steady increase in therapeutic use of DDN implies its clinical potential, its optimal use is yet to be established, largely due to the limited mechanistic understanding of its neurophysiological effects. This pilot project is our first step towards understanding the neurophysiological mechanisms of DDN, specifically the spinal mechanisms of DDN-induced plasticity. This project evaluates these mechanisms via two specific aims:

Aim 1. To evaluate the effects of DDN on proprioceptive reflexes in people with spasticity due to stroke.

In people with spasticity the excitability of the H-reflex pathway (an electrical analog of spinal stretch reflex) becomes elevated and reciprocal inhibition of the plantarflexors by the dorsiflexors becomes impaired (25, 26). Thus, to investigate the effects of DDN at the medial gastrocnemius (MG) MTrP on excitatory and inhibitory proprioceptive reflexes, in 20 individuals with spasticity due to stroke we will measure the H-reflex – M-wave (H/M) recruitment curves and reciprocal inhibition in the triceps surae muscles before, immediately after, 90 minutes after, 24 hours after, and 72 hours after DDN. One week prior to DDN, the same measurements will be repeated 5 times, with inter-measurement intervals matching to pre and post DDN measurements. We anticipate that decreases in H-reflex size and reciprocal inhibition will occur between pre and post DDN time points.

Aim 2. To evaluate the effects of DDN on cutaneous reflexes in people with spasticity due to stroke. Modulation of cutaneous reflexes to non-noxious stimulation of the skin become abnormal

post-stroke, reflecting the altered somatosensory processing in this population (33, 34). Thus, in this project, we will examine cutaneous reflex responses to non-noxious stimulation of the distal limb (i.e., at or below the area treated with dry-needling) at the same time points as the proprioceptive reflexes before and after a single DDN session. We anticipate that cutaneous reflex amplitudes will be decreased after DDN.

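### Post-hoc Bonferroni t-tests have no stated set of comparisons; four named pre-versus-post contrasts with Holm would serve the aims at least as well for the same familywise error

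*Combined protocol and SAP*

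**What the plan says.** Section 10.0 (Data Management, Data analysis) contains the whole multiplicity plan for the reflex outcomes. It opens with "For comparing reflex sizes before and after dry needling, a two-way repeated measures ANOVA", whose factors are studied side and time, and continues "together with Student t-test with Bonferroni correction as a post-hoc test". It gives no list of pairs, number of comparisons, alpha, sidedness or planned contrasts, and it does not say how many levels the time factor has.

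The questions and the schedule stand elsewhere. Aim 1 in section 1.0 reads "We anticipate that decreases in H-reflex size and reciprocal inhibition will occur between pre and post DDN time points". Aim 2 expects smaller cutaneous reflexes after DDN. Section 9.0 defines the DDN week as "one pre-DDN baseline and four post-DDN measurements: immediately after, 90 minutes, 24 hours, and 72 hours". There is also a matched control week: "One week prior to DDN, the same measurements will be repeated 5 times". Section 9.0 counts both weeks together: "during which measurements will be taken 10 times".

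**The concern.** The aims lead to four comparisons per outcome, each post-DDN time against pre-DDN. The analysis section does not tie the correction to those four, so the per-test threshold is undefined. Suppose the 24-hour contrast gave p = 0.008. That is significant if the correction covers four comparisons (0.0125) but not if it covers ten (0.005). Leaving this open until the data are seen weakens the error control that Bonferroni is meant to give.

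There is also a small question of efficiency. Once the family is fixed at four, Bonferroni is not the best choice at that familywise error, because Holm's step-down procedure rejects at least as much. The conclusions at individual times matter here. Section 1.0 says that the findings should help clinicians judge when to schedule training after DDN and should support later grant applications. With 20 participants there is little power to spare.

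**Working it through.** The plan has no power or sample-size figure to reproduce, so the check compares procedures under stated assumptions.

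**From the documents**
- n = 20, each participant measured repeatedly: "each of the 20 participants post stroke will participate in 7 visits over a two-week period".
- One pre and four post times in the DDN week; ten measurement times over both weeks.

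**Assumed, because the documents are silent**
- Familywise alpha 0.05, two-sided; 20 completers.
- Standardised paired change (mean change divided by the SD of change) between 0.3 and 0.8.
- Correlation between the four change scores 0.5, varied from 0.3 to 0.7.

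**Step 1: possible families**
- Four pre-versus-post pairs: 0.05/4 = 0.0125 per test.
- All pairs of the five DDN-week times: 5×4/2 = 10, so 0.05/10 = 0.005.
- All pairs of the ten times: 10×9/2 = 45, so 0.05/45 = 0.0011.

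**Step 2: power of one paired t-test with Bonferroni.** This is a noncentral t with 19 degrees of freedom and noncentrality d√20. At d = 0.7 the noncentrality is 0.7 × 4.472 = 3.13.

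| Family | Critical t | Power at d = 0.7 | Power at d = 0.5 | d for 80% power |
|---|---|---|---|---|
| 4 | 2.76 | 0.65 | 0.33 | 0.82 |
| 10 | 3.17 | 0.50 | 0.21 | 0.91 |
| 45 | 3.84 | 0.29 | 0.09 | 1.07 |

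**Step 3: Holm on the four contrasts.** Order the four p-values. Compare the smallest with 0.05/4, the next with 0.05/3, then 0.05/2, then 0.05, stopping at the first failure. Four correlated paired t-tests were simulated (100,000 replicates per scenario, correlation 0.5).

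| True effects (SD) | Bonferroni over 4 | Holm over 4 |
|---|---|---|
| 0.7 at all four, average per contrast | 0.65 | 0.75 |
| 0.5 at all four, average per contrast | 0.33 | 0.40 |
| 0.8 / 0.7 / 0.5 / 0.3, average per contrast | 0.47 | 0.54 |
| 0.7 at one time only, power at that time | 0.65 | 0.65 |
| 0.7 at all four, at least one detected | 0.91 | 0.91 |
| None, familywise error | 0.043 | 0.043 |

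For the fading case, the Bonferroni average is (0.785 + 0.647 + 0.331 + 0.103)/4 = 0.47 and the Holm average is (0.812 + 0.700 + 0.434 + 0.204)/4 = 0.54. With 0.7 SD at all four times, Holm's average stays at 0.74 to 0.76 for correlations from 0.7 down to 0.3.

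**Step 4: why the gain is uneven.** Holm's first step is the Bonferroni threshold itself, so the chance of detecting at least one effect cannot change. The later, easier thresholds help only after an earlier rejection, so they add almost nothing when a single effect is real.

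**The case against.** The strongest reply is that the plan already implies four comparisons. The analysis sentence is framed as before against after needling, and Aim 1 speaks of changes that "will occur between pre and post DDN time points". On that reading Bonferroni is valid, Holm adds nothing to the chance of finding some effect, and the change is a modest refinement in a pilot. Much of this stands: pre-versus-post is the more natural reading. What remains is that the family is nowhere stated and that Holm on the same four cannot do worse.

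A reader might infer that the correction covers all 10 pairs of the five DDN-week times, and so that power per time falls to 0.50 against 0.75 for Holm at 0.7 SD. The documents do not support this. They never say that all pairs will be tested, and section 10.0 does not fix a five-level time factor.

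A reader might also infer that the switch is free. That is true of familywise error only. Comparisons among the post times bear on when an effect peaks or fades, which section 1.0 cares about, and they would become descriptive. Holm also has no simple matching simultaneous intervals.

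It is also fair to object that equal effects of 0.7 SD at all four times favour Holm. Section 1.0 speaks of temporary relief, so the fading case deserves equal weight. The calculation also leaves out the side factor and the omnibus test.

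**Conclusion.** The point holds in a limited form. What is certain is that the post-hoc family, alpha and sidedness are not stated, although the aims imply four comparisons per outcome. Given those four, Holm is never less powerful than Bonferroni, and this needs no assumption about effect size.

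The size of the gain does rest on assumptions. With 20 completers and a two-sided familywise alpha of 0.05, it is about 10 percentage points per contrast at 0.7 SD throughout and about 7 points in the fading case. It is essentially zero if only one effect is real, and zero for detecting at least one. The lower starting power of 0.50 at 0.7 SD would apply only if all 10 pairs had been intended. If change is measured against the control week, the same four-test structure applies, but the standardised effects depend on variances that the documents do not give.

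**What to change.** In section 10.0, replace the post-hoc phrase with wording such as:

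*For each reflex outcome on the treated side, four planned contrasts will be tested: immediately, 90 minutes, 24 hours and 72 hours after DDN, each as change from pre-DDN (relative to the matched control-week change, if that is what the model estimates). Tests are two-sided, with Holm step-down at familywise 0.05 within the outcome. All other pairs are descriptive, with confidence intervals.*

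State also whether the contrasts are tested regardless of the omnibus F test.

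The change costs one sentence and needs no extra participants, visits or measurements. Post-versus-post pairs lose confirmatory status; if one of them matters for the time course, it should be named and added to the family. Because Holm lacks simple simultaneous intervals, report Bonferroni intervals beside the Holm p-values. The familywise 0.05 applies within one outcome only. Multiplicity across muscles, nerves, stimulus intensities and latency epochs (section 9.0) is not covered and needs its own statement.

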Additionally, to interpret these reflex changes related to typical clinical measures, we will measure passive and active dorsiflexion range of motion (ROM) and the Modified Ashworth scale, Fugl-Meyer, and 10-m walk test. These measurements will facilitate the development of future DDN clinical trials towards establishing spinal neurophysiological mechanisms of DDN.

The findings from this project would also help clinicians estimate when post DDN motor practice/training therapies should be administered for improving motor function in persons with and without spasticity. The data obtained through this pilot project will significantly strengthen our future NIH R-series applications, through which we plan to test the hypothesis that a single administration of DDN procedures will produce lasting effects on spinal neurophysiology that support temporary relief/alleviation of sensorimotor impairments in people with spasticity due to chronic stroke.

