4.0 Inclusion and Exclusion Criteria/ Study Population

Adults (≥ 18 years old) with spastic hyperreflexia due to stroke.

Inclusion criteria are: 1) neurologically stable for >6 months (and >1 yr post stroke); 2) medical clearance to participate; 3) unilateral ankle and/or wrist spasticity, confirmed by Modified Ashworth Scale (MAS) > 1 and the presence of spastic hyperreflexia, 4) ability to ambulate at least 10 m with or without an assistive device (except for parallel bars). For quantifying hyperreflexia, we will measure the H-reflex in the soleus for the lower extremity. We will enroll post-stroke individuals who exhibit abnormally large H-reflexes [25] and abnormally strong reflex activity during the simple motor task [26,72,73] (e.g., walking and reaching and grasping). The H-reflex is completely suppressed in neurologically normal individuals during the swing phase of walking [74], for example, and therefore, testing reflexes during these dynamic movements is useful for evaluating spasticity.

Exclusion criteria are 1) motoneuron injury (i.e. the neurons that give rise to the axons innervating the muscles) with inadequate response to stimulation; 2) a cardiac condition (history of myocardial infarction, congestive heart failure, pacemaker use, coronary artery disease, atrial fibrillation, congenital heart disease, uncontrolled hypertension); 3) a medically unstable condition

(including temporary infections and pregnancy); 4) age <18 years old; 5) cognitive impairment sufficient to interfere with informed consent or successful completion of the protocol; 6) metal allergies; 7) needle phobias; 8) lymphedema over a limb (due to risk of infection/cellulitis); 9) abnormal bleeding tendencies; 10) compromised immune system; 11) vascular disease; 12) uncontrolled diabetes; 13) history of epilepsy (as DDN generates strong somatosensory sensation); 14) anxiety disorders or in distress; 15) botox injection in targeted muscle within 3 months prior to study procedures.

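### The reflex ANOVA uses a side factor for which no second leg is recorded and omits the control-week contrast; a descriptive t-test also has no comparison group

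*Combined protocol and SAP*

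**What the plan says.** **Analysis (Section 10.0, Data analysis).** Reflex sizes around needling are to be compared with "a two-way repeated measures ANOVA (studied side of the extremity" by time, followed by Bonferroni-corrected t-tests. A separate Student t-test is planned "For simple comparison between participants without known neurological conditions and participants after stroke", with age and maximum M-wave as examples.

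**Who is enrolled.** Section 5.0: "Twenty adults (≥ 18 years old) with spastic hyperreflexia due to stroke are recruited". Section 4.0 requires "unilateral ankle and/or wrist spasticity, confirmed by Modified Ashworth Scale (MAS) > 1 and the presence of spastic hyperreflexia". Sections 7.0 and 9.0 likewise describe only people after stroke.

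**What is recorded.** Section 9.0 places the EMG electrodes over tibialis anterior, both gastrocnemii and "soleus muscles of the studied leg". DDN is given once, to the medial gastrocnemius. Pain and range of motion are taken in the affected limb.

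**How the study is controlled.** Sections 1.0 (Aim 1) and 9.0 describe five measurements in an untreated first week, at intervals matching the five in the DDN week. The DDN-week measurements are one before needling and four after it (straight away, 90 minutes, 24 hours, 72 hours). Each person acts as their own control.

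**The concern.** Reflex size is the outcome of both aims, and Section 10.0 names only one model for it. The second factor in that model does not match anything the protocol schedules, while the factor the study was built around, control week against DDN week, does not appear.

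An analyst following the text literally would find that side cannot be estimated, or would fit it as a left/right grouping of participants that says nothing about DDN. Either way, the control week could be collected and then left out of the formal test. A fall in reflex size after needling could then not be separated from the drift that repeated testing over 72 hours might produce on its own, which is what the control week is there to measure.

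The intact-versus-stroke t-test is a smaller inconsistency in the same paragraph: a listed analysis with no described data source.

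**Working it through.** **1. The plan's own count.** Measurements: 5 (control week) + 5 (DDN week) = 10, as Section 9.0 states. The 20 participants come with no power calculation, so there is no sample-size figure to reproduce.

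**2. The side factor, under each available reading** (n = 20, t = 5 times)

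| Reading of side | Side df | Side × time df | What it compares |
|---|---|---|---|
| One studied leg per person, as Section 9.0 describes | 1 − 1 = 0 | 0 × 4 = 0 | Nothing; only time is testable, on 4 and 19 × 4 = 76 df |
| Left or right studied leg, varying between people | 1 and 20 − 2 = 18 | 4 and 18 × 4 = 72 | People studied on the left with people studied on the right |
| Needled and un-needled leg of the same person | 1 and 19 | 4 and 76 | A within-person contrast, but no recording on the other leg is described |

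Design-matrix check: participant and time effects have rank 20 + 5 − 1 = 24. Adding a constant side column leaves the rank at 24. Adding a left/right column also leaves it at 24, because that column is a combination of the participant effects. Under the left/right reading, only its interaction with time is estimable within people, and that interaction does not concern DDN.

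**3. Does time alone recover the control week?** Time restricted to the DDN week has 4 and 76 df and does not use the control week. Time over all ten measurements has 9 and 19 × 9 = 171 df. Those 9 df contain the week contrasts (1 for week + 4 for time within week + 4 for their interaction), but the overall test does not isolate them and Section 10.0 specifies no contrast.

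**4. The model that matches the design:** week (2) × time (5), both within person, 20 complete participants.

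- Week: 2 − 1 = 1 df; error 1 × 19 = 19.
- Time: 4 df; error 4 × 19 = 76.
- Week × time: 1 × 4 = 4 df; error 4 × 19 = 76.
- Check: 20 × 2 × 5 = 200 observations, so 199 df in total; 19 (participants) + 1 + 19 + 4 + 76 + 4 + 76 = 199.

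The interaction asks whether change from the week's first measurement differs between the weeks. The week main effect is not the test of DDN, because it averages in the pre-needling measurement.

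**5. The intact-group t-test.** Group sizes are 20 and 0, so the statistic, its df and its p-value are undefined.

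**The case against.** The strongest reply is that these are loose phrases, and that the control is stated clearly elsewhere. Several parts of it stand.

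- **The control is not hidden.** Sections 1.0 and 9.0 say plainly that each person is their own control. A reader might infer that the protocol promises an untreated leg or a healthy group as a control for time; no section does.
- **The control week is not the only comparator.** A reader might infer that it is, but Section 9.0 also has a pre-DDN baseline, and Aim 1 frames the expected effect as pre to post. The repair should use both.
- **The intact comparison is minor.** It is called simple, and its examples are age and maximum M-wave. It serves neither Aim 1 nor Aim 2.
- **Unilateral spasticity does not prove that one leg is recorded.** The other leg would be available. The evidence is the EMG description and the absence of any scheduled second-leg recording.
- **Lost degrees of freedom are not the harm.** Moving from 76 to 72 error df changes the 5% critical F on 4 numerator df only from 2.492 to 2.499.
- **There is no formal conclusion about people without spasticity.** Section 1.0 says the findings could help time therapy "for improving motor function in persons with and without spasticity". One could read that as a claim the trial cannot support, but it is an anticipated use, not a hypothesis or planned test; at most it is a minor wording limit.

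None of this gives side a contrast that tests DDN, or puts week into the named model.

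**Conclusion.** The point holds for the analysis text. As written, the only reflex model has a second factor that is either inestimable (0 df) or irrelevant to DDN, and it omits the contrast between control week and DDN week. That affects the main test for both aims. The intact-group t-test cannot be run, with no consequence for either aim.

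This rests on the recordings being as Section 9.0 describes them. If reflexes are in fact recorded on both legs, the protocol needs to say so, and side would then be a usable factor. The df quoted assume 20 participants with all ten measurements and no sphericity correction.

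Even the corrected model carries one assumption: because the control week always comes first, the interaction attributes to DDN any difference in within-week profile between first and second week. The wording change cannot remove that, but it does make use of the control data collected.

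**What to change.** In Section 10.0 (Data analysis):

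1. Replace side with week (control or DDN), giving a within-person week × time model with 2 × 5 levels.
2. Name the week × time interaction, expressed as change from each week's first measurement, as the test of the DDN effect. The Bonferroni-corrected t-tests can stay, applied to the between-week difference in change at the four later times.
3. Report which leg was studied descriptively.
4. Delete the t-test of intact people against people after stroke. If the sponsor means to draw an intact group from other data, the source and numbers would have to be stated instead.

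The cost is protocol wording. All the data are already scheduled; no visit, measurement or participant is added, and no clinical procedure changes.
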